The purpose of this study was to build upon our community-based participatory research (CBPR) partnerships with the [tribal name] tribal community to culturally adapt an evidence-based, indicated PEI program for universal delivery with 8-12-year-olds living on the [tribal name] Reservation using a systemic, theory- and culturally-grounded qualitative approach. In addition, we will use a mixed methods approach to evaluate the feasibility of delivering the adapted PEI in two tribe-serving schools and estimated effect sizes of changes in anxiety and depression from pre- to post-intervention using single-group design (i.e., no control group). We also aimed to determine the extent to which the program was acceptable and enjoyable for [tribal name] youth.

Research Design

Our study involved two major phases:

- 1) a qualitative phase, which included collaboration between the CAB and research team that resulted in a conceptual framework for cultural adaption of the PEI program, gathering suggestions for cultural adaptations and to improve the PEI program from focus groups with key adult stakeholders in the [tribal name] community (Elders, parents, teachers, and mental health specialists) and youth stakeholders, and the CAB making cultural adaptions to the PEI program based on the focus group data.
- 2) a clinical trial phase, which included delivery of the adapted intervention in two tribal serving schools for the [tribal community name] Reservation using a pre-post, single group design (i.e., no control group). We evaluated feasibility and acceptability using youth and provider self-report data and estimated the effect sizes of changes in youth anxiety and depressive disorder symptoms using youth and teacher reports. In addition, we gathered survey data on youth resilience, anxiety control beliefs, and rumination.

Cultural Adaptation of the PEI Program (Phase 1)

Development of Conceptual Framework and Review of the PEI program (Step 1)

In Year 1, the 8-10 member CAB (Elders, parents, teachers, mental health professionals, cultural experts) and research team met once a month and engaged in several activities throughout Step 1 described in this section and Step 3 described in a later section. All CAB members completed a

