At the end of Year 2, the CAB and research team met to review all grouped suggestions gathered from the WGs and FGs. The CAB identified and integrated modifications or additions to our conceptual framework if needed based on the FG feedback. Next, the CAB reviewed the content, format, and learning objectives of each of the six PEI program modules and training protocol within the context of this finalized conceptual model. Specifically, the CAB identified the type of change needed (e.g., content, language, learning strategy), amount of change required (no change, small change, moderate change, large change), and barriers (timeline/budget). The CAB decided on the importance of the change (essential or non-essential), made final decisions on adaptations, and the physical adaptations of the PEI program materials were made by the developers of PEI as requested by the CAB.

Adapted PEI Program Intervention Evaluation (Phase 2; Clinical Trial)

In Year 3, The CAB worked with the research team to culturally adapt the intervention and identified two school counselors (i.e., an American Indian tribal member and a white non-tribal member) to provide it in the schools. Both providers completed the modified PEI program training based on CAB decisions for adaptation and the CITI Training (through Montana State University-Bozeman) before working with youth in the school. They also completed a background check for each school. Providers recorded youth attendance, dropout of the intervention, and completed the Brief Reactions Form for after each session.

In Year 3, we recruited 28 Native youth ages 8-12 years-old from the [two tribal serving school names] (15 youth per school) to participate in the adapted PEI program. The adapted PEI program was delivered to a group of 3-5 youths at one time with three groups participating in each school. Written informed consent was obtained from the parents or legal guardians before youth participated in the intervention or complete pre- and post-survey assessments. Youth participants also provided written assent before completing the pre-intervention and post-intervention surveys or participating in the adapted PEI program.

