Youth participants completed the pre-intervention survey (~30 minutes to complete based on our pilot study) one week before session 1 and the post-intervention survey one week after session 6 of the adapted PEI program. The post-adaptation usability survey was administered at the end of each session. Youth completed the survey using paper and pencil. The research team explained the purpose of the study and intervention. They also read the assent form out loud to youth and answered any questions youth had about the study. Those youth who verbally agreed and checked “yes” on the assent form completed the youth survey and participated in the intervention. Youth who choose not to participate in the study returned to their classroom. All youth were notified of their right to withdraw the study and intervention at any time without consequence. The research team helped youth who may have difficulty comprehending items or response options.

Youth Assessments. The CAB reviewed and approved the following instruments as being culturally appropriate (minor changes were made to existing measures) for our previous study

with 71 Native 8-13-years-old at the [tribal school name]. Each measure showed acceptable to excellent reliability and both convergent and discriminant validity with other established measures in that study (Scott, [name], Small, & McCullen, 2023).

Youth Demographics. We asked children to provide personal information including gender, age, ethnicity, tribal affiliation, grade level, and family structure.

Revised Child Anxiety and Depression Scales – Short Child Version (RCADS-SC).^{37,38} The RCADS-SC is a 25-item self-report instrument used to assess DSM-IV criteria (APA, 1994) of symptoms for anxiety disorders (excluding Posttraumatic Stress Disorder and Specific Phobias) and depression. We asked the children to rate how often each anxiety and depression symptom is true of them on a rating scale consisting of: 1 (Never), 2 (Sometimes), 3 (Often), and 4 (Always). Higher scores represent the experience of more anxiety and depression symptoms as based upon the DSM-IV criteria.

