Study Aim 2: Evaluate the feasibility and acceptability of the culturally adapted PEI program. We calculated the frequency of youth attendance rates across sessions, dropout rates, and survey response rates. We also created tabular summaries of the Likert scale ratings from the usability survey and proportion of respondents who rated each module or all modules on average as 2 or 3. A module or the entire program was successfully adapted if at least 80% of youth rated it as a 2 or 3 on the Likert scale for acceptability and enjoyability.

Study Aim 3. Estimate effect size changes in anxiety and depressive symptoms in [tribal name] youth. Primary outcomes of interest for a future efficacy trial will be changes in the RCADS-S scales. For each scale, we computed the change in the scale score from baseline to post-intervention (post – pre) and computed unadjusted averages and standard deviations. A one-sample t-test of the changes in any response scale will have 80% power to detect a standardized effect size (Cohen's d) of at least 0.53, and 90% power to detect an effect size of at least 0.61. We will also obtain adjusted estimates using mixed effects linear regression models of post-test score on pre-test score with demographic factors and random effects for school and intervention group nested within school. This will allow us to estimate intra-class correlations for intervention group and schools, which will be required for sample size estimation in a full efficacy trial.

INSTITUTIONAL REVIEW BOARD AMENDMENTS

The following pages (not numbered, but in order of date) contain tribal college IRB amendments that were submitted and approved throughout the study period.

February 9, 2021

Dear [tribal college] IRB,

We are requesting a minor modification for the approved study titled, "A Native Path to Courage." We have outlined the modification below.

- 1) We plan on using a professional online transcription service (Rev.com) to transcribe work and focus group data. The company uses state-of-the-art encryption procedures for audio files to be uploaded and all professional transcribers are required to sign nondisclosure and confidentiality agreements (<https://www.rev.com/enterprise/security>). In addition, we can request for all audio files to be removed from their servers after transcription is complete. We will remove names from the transcription documents upon receipt. Only first names are mentioned in the audio recordings.

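### In a single group, does the planned post-on-pre mixed model fail to give the adjusted change that Aim 3 needs?

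*Combined protocol and SAP*

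**What the plan says.** The SAP (Statistical Analysis Plan for Phase 2, Study Aim 3) sets the target: "Estimate effect size changes in anxiety and depressive symptoms". For each RCADS-S scale the investigators "computed the change in the scale score from baseline to post-intervention", and they report unadjusted means and SDs of that change. The power statement refers to a one-sample t-test of the same change.

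The SAP then adds the adjusted analysis: "We will also obtain adjusted estimates using mixed effects linear regression models of post-test score on pre-test score with demographic factors", with "random effects for school and intervention group nested within school". The one use it goes on to state for this model is: "This will allow us to estimate intra-class correlations for intervention group and schools", as input to the sample size of a later efficacy trial.

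The Research Design section makes this a pre-post study of one group without a control. The Phase 2 section gives 28 recruited youth, with the program "delivered to a group of 3-5 youths at one time with three groups participating in each school", so six groups in two schools. The SAP does not say which demographic items enter the model, whether covariates are centred, which quantity is the adjusted estimate, or what interval and degrees of freedom go with it.

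**The concern.** In a two-arm trial, regressing post-test on pre-test gives a treatment coefficient, and that is the adjusted estimate. Here there is no second arm. The fixed effects are an intercept, a pre-test slope and demographic slopes, and none of these is a change. If pre-test enters uncentred, the intercept is the expected post-test at a pre-test score of 0. That score cannot occur on 25 items each scored from 1 to 4, whose sum is at least 25.

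Two things would be at stake. Analysts could report different quantities under one label: an intercept, an adjusted post-test mean, or a recovered change. And if a change is recovered, its model standard error treats the baseline mean as fixed. That could overstate precision in figures meant to plan an efficacy trial.

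**Working it through.** **The plan's own figure.** The SAP gives detectable effects of d = 0.53 at 80% power and 0.61 at 90%. With an exact one-sample t-test, n = 30 and two-sided alpha 0.05 (assumed, not stated), power is 80.1% and 89.8%, so the figures reproduce at the planned 15 per school. At the 28 recruited it is 77.1% and 87.5%. These figures concern the raw change and do not depend on the mixed model.

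**Step 1: is the change in the model?** Write the model as

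post = a + b·pre + c·z + school + group + error.

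Subtract pre from both sides:

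post − pre = a + (b − 1)·pre + c·z + school + group + error.

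This is the same model with the slope shifted by 1. Centre pre and z at their sample means and the intercept becomes the mean change at average covariates. Equivalently, take the centred intercept of the post-test model and subtract the baseline mean.

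Illustration (assumed: pre-test mean 45, SD 10 at both times, r = 0.5, change −2):
- slope 0.5; uncentred intercept 43 − 0.5 × 45 = 20.5
- centred intercept 20.5 + 0.5 × 45 = 43
- recovered change 43 − 45 = −2

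**Step 2: does it differ from the raw change?** In ordinary regression the centred intercept is the post-test mean, so the recovered change equals the raw mean change exactly, whichever demographics are chosen. With random effects and unequal groups it can move. Simulation inputs, all assumed except n and the number of groups: n = 28; six groups of 5, 5 and 4 per school; r = 0.3, 0.5, 0.7, 0.8; group variance 0 or 0.1 and school variance 0 or 0.05 of the score variance; age and sex as covariates; REML; 4,004 runs in each of 12 settings. The mean absolute gap was 0.002–0.007 SD and the largest 0.08. With groups of 5, 5, 5 and 5, 5, 3, also allowed by the protocol, the mean gap under clustering was 0.012–0.015 SD and the largest 0.14.

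**Step 3: the standard error.** Without clustering, the variance of a change is 2σ²(1 − r), and the residual variance of post given pre is σ²(1 − r²). The ratio of standard errors is therefore √((1 + r)/2): 0.81, 0.87, 0.92, 0.95 for the four values of r. Simulated ratios and coverage of 95% z limits, for r = 0.3 / 0.5 / 0.7 / 0.8:

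| Assumed clustering | SE, post-on-pre ÷ change model | Coverage, post-on-pre (%) | Coverage, change model (%) |
|---|---|---|---|
| None | 0.81 / 0.87 / 0.93 / 0.96 | 91.7 / 93.1 / 94.6 / 95.5 | 96.0 / 96.5 / 96.3 / 96.2 |
| Group 0.1 | 0.86 / 0.91 / 0.96 / 0.98 | 90.4 / 92.1 / 91.7 / 92.1 | 94.3 / 94.7 / 93.1 / 92.9 |
| Group 0.1, school 0.05 | 0.87 / 0.93 / 0.97 / 0.98 | 87.6 / 87.9 / 86.8 / 87.2 | 92.1 / 90.7 / 88.3 / 87.8 |

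**Step 4: is that standard error too small?** Against the empirical SD of the estimate, the post-on-pre standard error was 0.96–1.17 times, and the change model's 1.02–1.23 times. A second check with 400 runs per setting gave 0.90–1.10 and 1.03–1.21. The SAP does not specify z limits, and with six groups t limits on 5 degrees of freedom are a sensible choice. With those, coverage was:
- no school variance: post-on-pre 96.1–98.4%, change model 97.2–98.9%
- school variance 0.05: post-on-pre 93.5–94.2%, change model 94.1–97.1%

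The 400-run check gave 93–98% for post-on-pre and 95–99.5% for the change model.

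**The case for a change.** The strongest case for a change is that the SAP should not leave its reader to work out what an adjusted estimate is. The text is silent on the contrast, the centring, the covariates and the degrees of freedom. A sentence or two would settle it, and the adjusted analysis is still written in the future tense. A mixed model with post minus pre as outcome and centred demographics would give the mean change as its intercept and would allow for sampling of the baseline mean. With z limits the post-on-pre model covers less in every setting above, by 0.6 to 4.5 percentage points.

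The silence is real, and so is the loss of coverage at low pre-post correlation with z limits. The rest is weaker:

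- The SAP nowhere says pre-test enters uncentred. The sentence before speaks of unadjusted averages of change, so an adjusted average change is the natural reading.
- The change model is not clearly better. Without school variance, 5-df limits leave post-on-pre nearer 95%. Without clustering, even z limits do so at r = 0.7 and 0.8 (94.6% and 95.5%, against 96.3% and 96.2%).
- Once schools differ, both models under-cover with z limits. The main cause there is having two schools and six groups.
- That the estimate adds little to the raw change applies to the alternative as well: mean gaps from the raw change were nearly identical (for example 0.0061 and 0.0059 SD).

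**Conclusion.** The SAP does not define its adjusted estimate, but this is missing detail that an analyst would fill sensibly. The planned model contains the adjusted mean change after centring, and that value sits within about 0.002–0.007 SD of the raw mean change (0.012–0.015 SD with a less even group layout under clustering). Moving to a change-score model would be a trade-off: intervals on average 2–23% wider (1/0.98 to 1/0.81), with no clear gain in calibration once small-sample limits are used.

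The effect size itself rests on the unadjusted mean and SD of change, which are fully specified. The intra-class correlations come from the model as written. No decision rule depends on the adjusted estimate. The sizes above rest on assumed pre-post correlations of 0.3 to 0.8 and assumed variance components, since the documents give neither. The algebra in Step 1 needs no such assumptions. No change to the plan is called for.

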To our knowledge, there are three culturally adapted interventions aimed at reducing anxiety and depression for AI youth. The *Cognitive Behavioral Intervention for Trauma in Schools (CBITS)* was culturally adapted for Northern Plains American Indian youth living on a

reservation with a history of trauma and post-traumatic stress disorder (PTSD) symptoms.^{23,24,29} They found pre- to post-intervention changes in PTSD, anxiety, and depression in 43 Northern Plains American Indian youth. However, they had low recruitment and retention rates (25% dropped out or left treatment). *FRIENDS* was culturally enriched for Canadian Indigenous 4th-6th graders using two Indigenous school board consultants and universal “surface” level changes, but did not find significant reductions in anxiety symptoms in 192 Indigenous youth using a wait-list control design.³⁰ *Coping with Depression for Adolescents* was culturally modified for American Indian students with community health professionals and educators and intended for adolescents with high levels of depression.²² Findings showed no differences from pre- to post-intervention for anxiety and depression between the treatment group and a treatment-as-usual control group.

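### Aim 3's unadjusted mean change is biased if loss to the post survey is related to baseline, and the SAP does not say at which baseline the adjusted model is evaluated

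*Combined protocol and SAP*

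**What the plan says.** The SAP for Phase 2, Study Aim 3, gives two estimates for each RCADS scale. For the first, the team "computed the change in the scale score from baseline to post-intervention (post – pre) and computed unadjusted averages and standard deviations". For the second, it plans "mixed effects linear regression models of post-test score on pre-test score", adjusted for demographics and with schools, and the groups inside them, as random terms, partly to obtain the intra-class correlations needed to size a later efficacy trial. The first is in the past tense; the second is worded as still to be done.

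Power is stated for "A one-sample t-test of the changes in any response scale". The lower target is "80% power to detect a standardized effect size (Cohen's d) of at least 0.53"; the higher target is "90% power to detect an effect size of at least 0.61". That sentence gives no sample size. The Phase 2 evaluation section reports 28 youth recruited, with 15 per school in parentheses.

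Loss is acknowledged elsewhere. Study Aim 2 tabulates dropout and survey response, youth may withdraw at any time, and the background says of an earlier adapted programme that "they had low recruitment and retention rates (25% dropped out or left treatment". Aim 3 itself states no analysis set, no missing-data rule or assumption, and no baseline value at which the adjusted estimate is evaluated.

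**The concern.** A change score needs both surveys, and a model with the post score as its only outcome has no row for a youth without one. Symptom change usually depends on the starting score: through regression to the mean, high scorers tend to fall more. If the youth who miss the post survey started higher or lower than the rest, the mean change among complete pairs is not the mean change for the enrolled group, even when loss depends on nothing but the recorded baseline. Losing higher-symptom youth understates the mean reduction; losing lower-symptom youth overstates it.

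The size of change is the main product of Aim 3, on scales that the SAP names as primary outcomes for a future efficacy trial. The baselines that would correct this part of the error have already been collected.

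**Working it through.** **The plan's own figure.** Inputs: d = 0.53 and 0.61 (SAP, Aim 3); two-sided alpha of 0.05 (assumed, as none is stated). Exact one-sample t-test power from the noncentral t:

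- n = 30 (15 in each of two schools): 80.1% and 89.8%, matching the stated 80% and 90%.
- n = 28 (recruited): 77.1% and 87.5%. The normal approximation at n = 28 gives detectable d of 0.529 and 0.613, which also round to the stated values.

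Either way, the stated power leaves no room for missing pairs. With 7 of 28 lost, leaving 21, power would be 63.7% and 75.8%. Below, d = 0.53 serves only as a yardstick.

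**Bias of the complete-pair mean change.** Let r be the pre-post correlation, g the baseline gap (lost minus kept, in baseline SD) and f the fraction lost. With equal pre and post SDs of 1 and loss depending only on baseline:

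- All-enrolled baseline mean minus complete-pair baseline mean = g × f.
- Expected change falls by (1 − r) per unit of baseline, so bias = (1 − r) × g × f.
- In change-SD units, divide by √(2(1 − r)).
- Standard error of the complete-pair mean = √(2(1 − r)/m), with m = 28(1 − f).

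The documents give none of r, g and f for this trial. Assumed: r = 0.4 to 0.7, g = 0.7, f = 10% to 25%.

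| f | r | Bias (baseline SD) | Bias (change SD) | Share of 0.53 | Standard error | Bias / SE |
|---|---|---|---|---|---|---|
| 10% | 0.4 | 0.6 × 0.7 × 0.10 = 0.042 | 0.042/1.095 = 0.038 | 7% | √(1.2/25.2) = 0.218 | 0.19 |
| 10% | 0.7 | 0.3 × 0.7 × 0.10 = 0.021 | 0.021/0.775 = 0.027 | 5% | √(0.6/25.2) = 0.154 | 0.14 |
| 25% | 0.4 | 0.6 × 0.7 × 0.25 = 0.105 | 0.105/1.095 = 0.096 | 18% | √(1.2/21) = 0.239 | 0.44 |
| 25% | 0.7 | 0.3 × 0.7 × 0.25 = 0.0525 | 0.0525/0.775 = 0.068 | 13% | √(0.6/21) = 0.169 | 0.31 |

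The range is therefore about 0.02 to 0.11 baseline SD. If f = 0 or g = 0, the bias is zero.

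**What happens to the adjusted model.** Let b be the fitted slope of post on pre. Leave out other covariates and clustering.

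- Evaluated at the complete pairs' mean baseline, the fitted post mean is their observed post mean. Subtracting their baseline mean returns the complete-pair mean change, bias included.
- Evaluated at the all-enrolled mean baseline, with that mean subtracted, the result is the complete-pair mean change − (1 − b) × g × f. This removes the bias term.

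**Simulation check.** Setup: 28 youth, 40,000 runs per scenario, no clustering, log-odds of loss rising by 0, 0.5 or 1.0 per baseline SD.

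| Loss, r, log-odds slope | Complete pairs: bias, SD, RMSE | Model at all-enrolled baseline: bias, SD, RMSE |
|---|---|---|
| 25%, 0.5, 0 | 0.000, 0.219, 0.219 | −0.001, 0.214, 0.214 |
| 25%, 0.5, 1.0 | 0.107, 0.215, 0.240 | 0.000, 0.220, 0.220 |
| 25%, 0.7, 1.0 | 0.063, 0.168, 0.179 | −0.001, 0.173, 0.173 |
| 10%, 0.7, 0.5 | 0.013, 0.155, 0.156 | −0.001, 0.155, 0.155 |

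The second row implies a gap of 0.107/(0.5 × 0.25) = 0.86 SD and a bias of half a standard error (0.107/0.215 = 0.50). In every scenario run, the post-on-pre slope and the fitted change at a fixed baseline were unbiased within 0.002.

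**The case against.** The case for leaving the plan alone has real force.

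- **No loss is documented.** Nothing in the documents reports a missing post survey among the 28 youth. The 25% is programme dropout in a trauma intervention for youth with post-traumatic symptoms, whereas this programme is delivered universally. It is not a rate of unreturned surveys. This stands, and 25% is used here only as an upper scenario.
- **The adjusted model already conditions on baseline.** A reader might infer that baseline-related loss biases both Aim 3 estimates because both omit youth without a post survey. The text does not support that. Omitting those youth does not distort the regression coefficients when loss depends only on baseline; only the choice of evaluation point can bring the bias back. What remains open is that the SAP does not state that choice.
- **The effect is modest.** Larger biases can be produced, up to 0.17 SD, but they need a baseline gap of about 1.1 SD together with 25% loss and a low correlation. In a single-group feasibility study, half a standard error or less will not dominate the uncertainty. This also stands.
- **Using every baseline is not a clear gain in precision.** With loss strongly related to baseline, the variance of the corrected estimate is slightly higher: (0.220/0.215)² = 1.05, or 5% more, in the second simulation row. Root mean square error was nevertheless equal or lower in every scenario.

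Aiming at all enrolled youth would still cost little more than a sentence in the SAP, and Aim 2's tabulation of loss makes it visible without correcting the Aim 3 estimate.

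**Conclusion.** The point holds for the unadjusted mean change. It holds for the adjusted mean change only if that is evaluated at the complete pairs' baseline mean. Under 10%-25% loss, correlation 0.4-0.7 and a 0.7 SD baseline gap, the bias is about 0.02-0.11 baseline SD. That is 0.03-0.10 in change-SD units, 5%-18% of the plan's d of 0.53, and roughly half a standard error or less. Loss rate, gap and correlation are all assumptions. With complete pairs, or loss unrelated to baseline, there is nothing to correct.

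A reader should not infer that this trial's results are biased. The documents show neither missing post surveys nor a link between loss and baseline. The finding is that the SAP leaves the Aim 3 estimate unprotected against a foreseeable and easily handled form of loss.

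**What to change.** Keep the planned mixed model, with its group and school random effects and the intra-class correlations it is meant to supply. Add to the SAP:

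1. State who enters each Aim 3 analysis.
2. For each RCADS scale, evaluate the adjusted post mean at the mean baseline of all enrolled youth, with demographic factors likewise at their all-enrolled means. Subtract that baseline mean and report the result as the Aim 3 mean change.
3. Give a 95% CI that allows for clustering by group and for estimation of the baseline mean, for example by adding (1 − b)² times the variance of the all-enrolled baseline mean to the model-based variance.
4. Keep the complete-pair mean and SD as description.
5. Tabulate baseline scores of youth with and without a post survey.

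Stacking pre and post as two outcomes with shared random intercepts should not replace the planned model. Those intercepts cancel from the time effect, so its CI ignores clustering of change by group. With six groups and complete data, coverage was about 90% at an assumed change ICC of 0.10 and 86% at 0.20. Its group ICC would also describe symptom level rather than the baseline-adjusted outcome.

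The cost is a little more analysis and, when loss is strongly related to baseline, slightly higher variance with root mean square error no worse. No new data are needed. Loss that depends on the unseen post score remains uncorrected, and the report should say so.
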